#### **Additional Evaluations:**

Additional clinical laboratory evaluations will be performed at other times if judged to be clinically appropriate or if the ongoing review of the data suggests a more detailed assessment of clinical laboratory safety evaluations is required. Any changes to the scheduled times of clinical laboratory determination will be agreed between the investigator and Vertex and documented in the study master files.

#### **11.6.3 Physical Examinations and Vital Signs (Ivacaftor Arm Only)**

A PE of all body systems and vital signs assessment will be performed at screening and select study visits. At other visits, symptom-directed PEs and symptom-directed vital sign assessments can be performed at the discretion of the investigator or health care provider.

A PE includes a review of the following systems: head/neck/thyroid; eyes/ears/nose/throat (EENT); respiratory; cardiovascular; lymph nodes; abdomen; skin; musculoskeletal; and

neurological. Anorectal and genital examinations will be performed when medically indicated. After screening, any clinically significant abnormal findings in PEs will be reported as AEs.

The abbreviated PE will include an assessment of the following body systems: head/neck/thyroid, EENT, cardiovascular system, respiratory system, skin, and abdomen.

Vital signs include blood pressure (systolic and diastolic), temperature, heart rate, respiratory rate, and pulse oximetry. The subject will be instructed to rest in the supine position (if possible) for at least 5 minutes before vital signs are assessed. The temperature must be obtained by the same method throughout the study.

#### **11.6.4 Electrocardiograms (Ivacaftor Arm Only)**

Standard 12-lead ECGs will be performed using a machine with printout. Additional standard 12-lead ECGs will be performed at any other time if clinically indicated. The performance of all ECGs will adhere to the following guidelines:

- The subject will rest in the supine position for at least 5 minutes, if possible, before having an ECG performed.
- The ECG will be performed predose through the Week 24 Visit before any other procedures that may affect heart rate, such as blood draws. Following the Week 24 Visit, ECGs may be taken pre- or post-dose.

The ECG traces will be manually read at the study site at the Screening Visit and Safety Follow-up Visit. A printout of the ECG traces will be made for safety review by the investigator and maintained with source documentation. Clinically significant ECG abnormalities occurring during the study through the Safety Follow-up Visit will be recorded as AEs.

Study sites should use QTcF unless they receive approval in advance from the Vertex medical monitor or authorized designee to use QTcB.

To ensure safety of the subjects, a qualified individual at the study site will make comparisons to baseline measurements. If the QTcF is increased by >60 msec from the baseline or an absolute QTcF value is  $\geq 500$  msec for any scheduled ECG, 2 additional ECGs will be performed approximately 2 to 4 minutes apart to confirm the original measurement. If either of the QTcF values from these repeated ECGs remains above the threshold value (>60 msec from baseline or  $\geq 500$  msec), a single ECG will be repeated at least hourly until QTcF values from 2 successive ECGs fall below the threshold value that triggered the repeat measurement. A subject with a QTcF value above the threshold value will discontinue dosing.

#### **11.6.5 Ophthalmologic Examinations**

All subjects should have an OE approximately every 24 weeks while on ivacaftor treatment in this study. Subjects who did not participate in Study 124 Part B should have an additional OE exam at Week 12. The OE must be conducted by a licensed ophthalmologist, preferably a pediatric ophthalmologist. Whenever possible, the same ophthalmologist should perform the OEs throughout the study. The OE will include the following:

- Examination of the lens with a slit-lamp (portable or otherwise; pharmacologically dilated examination)
- Assessment of the red reflex (pharmacologically dilated examination)

- Screening OEs (subjects not from Study 124 Part B only): examination of the fundus (retina, optic nerve, and vessels), pupils, and eye movements

For subjects not from Study 124, relevant medical history (e.g., history of steroid use; history of trauma to the eye; and family history of glaucoma, congenital cataracts, or cataracts arising later in life) will be collected at screening. For subjects from Study 124 Part B with a Same-day Transition, the above relevant ophthalmological medical history will be collected in Study 124. For subjects from Study 124 Part B with a Gap Transition, the above relevant ophthalmological history will be collected before or at the Day 1 Visit.

During the screening period, if an adequate slit-lamp examination cannot be conducted, subjects will not be enrolled until an adequate repeat slit-lamp examination is completed (Sections 9.1.1.1.1 and 9.1.1.1.3) and eligibility criteria regarding the ophthalmologic findings are met.

If a new lens opacity or cataract is identified at any OE in subjects in the ivacaftor arm, study drug dosing must be discontinued. The-Vertex medical monitor should also be notified.

## **12 STATISTICAL AND ANALYTICAL PLANS**

Analysis of all data will be performed by Vertex (or designee).

A detailed analysis plan for the analysis of safety and efficacy data will be presented in a statistical analysis plan (SAP). As the study design is open label, a draft SAP for the final analysis will be available before the first subject is dosed; the SAP will be approved before data lock.

### **12.1 Sample Size and Power**

The study is not powered to detect a significant treatment effect. The study will enroll approximately 75 subjects.

### **12.2 Analysis Sets**

The All Subjects Set (defined as all enrolled subjects) will be used to summarize the disposition table and listings. The Safety Set (defined as enrolled subjects who receive at least 1 dose of ivacaftor in Study 126) will be used for all safety analyses. The Full Analysis Set (FAS) (defined as enrolled subjects who have at least 1 postbaseline efficacy assessment in Study 126) will be used for all efficacy analyses.

### **12.3 Statistical Analysis**

Data from all endpoints will be summarized using descriptive statistics and presented by subjects from Study 124 Part B/subjects not from Study 124 Part B, and by study visit. No inferential analyses are planned.

#### **12.3.1 General Considerations**

All individual subject data, including derived variables, will be presented in the data listings, which will include data for all subjects included in the study from all of the analysis sets. All analyses will be performed using SAS® (SAS Institute, Cary, North Carolina, USA).

Continuous data will be summarized using descriptive statistics.

Categorical data will be summarized by contingency tables (n, percentage, and 95% CI).

Listings will display all subjects who were enrolled or dosed.

Definition of the baseline value: There are 2 baselines, the baseline from Study 124 Part B and the baseline in the current study.

The Study 124 Part B baseline value will be defined as the baseline measurement from Study 124 Part B. That is, the most recent non-missing measurement collected on or before the initial administration of study drug in Study 124 Part B will be the Study 124 Part B baseline. This definition applies to both scheduled and unscheduled measurements; if an unscheduled value is the most recent non-missing measurement, it will be taken as baseline.

The Study 126 baseline value will be defined as the most recent non-missing measurement collected on or before the initial administration of study drug or enrollment in the observational arm, including both the scheduled and unscheduled measurements.

The absolute change from baseline value will be defined as the postbaseline value minus the baseline value.

For subjects from Study 124 Part B with a Same-day Transition (Section 9.1.1.2.1), absolute change will be determined from Study 124 Part B baseline and Study 126 baseline. For subjects from Study 124 Part B with a Gap Transition (Section 9.1.1.2.1), absolute change will be determined from Study 126 baseline.

For subjects who did not participate in Study 124 Part B (e.g., subjects from Study 124 Part A or subjects not from Study 124), absolute change will be determined from Study 126 baseline.

The definitions will apply to all analysis variables: demographics, medical history (including prior and concomitant medications), baseline characteristics, efficacy, and safety, unless otherwise specified.

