**Table 3-2 Schedule of Assessments for VX15-770-126 (Ivacaftor Arm: Gap Transition Subjects From Study 124 Part B)**

Event/Assessment	Treatment Period (Day 1 through Week 96)				ETT Visit a	Safety Follow-up Visit b	24-Week Follow- up OE
	Day -28 to Day -1	Day 1 c	Weeks 12, 36, 60, and 84 (±7 Days)	Weeks 24, 48, 72, and 96 (±7 Days)	As Soon as Possible After the Last Dose	4 Weeks (±7 Days) After the Last Dose	24 Weeks (+ 14 Days) After the Last Dose
Informed consent d	X	X					
Reconfirm eligibility	X	X					
Medical history e	X						
Clinic visit	X	X	X	X	X	X	
Study drug dose determination f		X	X	X			
Length and weight g		X	X	X	X	X	
Physical examination h		X	X	X	X	X	
Vital signs i		X	X	X	X	X	
12-lead ECGs l,j		X		X	X	X	
Serum chemistry and hematology	X k		X	X	X	X	

- a The ETT Visit is to be scheduled as soon as possible after the last dose of ivacaftor. If the ETT Visit occurs 3 weeks or later after the last dose of ivacaftor, the Safety Follow-up Visit will not be required. Subjects who elect to receive commercially available ivacaftor will be discontinued from ivacaftor dosing and will complete the ETT Visit and Follow-up OE.
- b For subjects who elect to receive commercially available ivacaftor, the Safety Follow-up Visit will not be required.
- c The Day 1 Visit will not be the same day as the last study visit of Study 124 Part B. All Day 1 assessments will be conducted on Day 1 with the possible exception of the serum and hematology assessments and the OE, as detailed in footnotes **k** and **m**. If the Day 1 Visit is ≤9 days after the last study visit of Study 124 Part B, the subjects must sign the ICF and confirm eligibility before dosing on Day 1.
- d Subjects must sign the ICF before undergoing any study-related assessments.
- e Medical history only applies to subjects that complete a Study 124 Safety Follow-up Visit and only for new conditions that start after the Study 124 Safety Follow-up Visit and prior to the Study 126 Screening Visit.
- f The ivacaftor dose for each subject will be reassessed based on body weight and adjusted if necessary (see Section 9.4).
- g Length and weight measurements will be performed predose through the Week 24 Visit (see Section 11.5.1).

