8 STATISTICAL ANALYSIS

8.1 General Considerations

The Schedule of Assessments is provided in [Appendix A](#). The precision standards for reporting safety and efficacy variables are provided in an internal Biometrics document that specifies the programming rules including the precision for derived variables.

All individual subject data for subjects who are enrolled in the current study will be presented in individual subject data listings.

As no subjects are enrolled in the Observation Arm, all analyses will be done for subjects from the Ivacaftor Arm only. All analysis will be performed for the Ivacaftor Arm overall, unless otherwise specified.

Continuous variables will be summarized using the following descriptive summary statistics: the number of subjects (n), mean, standard deviation (SD), standard error (SE), median, minimum value (min), and maximum value (max). 95% confidence intervals (CI) may be provided as appropriate.

Categorical variables will be summarized using counts and percentages. 95% CI may be provided as appropriate.

Baseline value is defined in two different ways:

Study 124 baseline: the baseline value for rollover subjects (who participated in Study 124 Part B or Part A/B) is defined as the baseline measurement from Study 124 Part B or Part A/B. That is, the most recent non-missing measurement collected on or before the initial

administration of study drug in Study 124 Part B or Part A/B. Note that this definition is consistent with the definition of baseline in Study 124 and applies to both scheduled and unscheduled measurements; if an unscheduled value is the most recent non-missing measurement, it will be used as baseline.

Study 126 baseline: the baseline value for IVA-naïve subjects (who did not participate in Study 124 Part B or Part A/B) is defined as the most recent non-missing measurement collected on or before the initial administration of study drug in the current study, including both the scheduled and unscheduled measurements.

Change (absolute change) from baseline will be calculated as Postbaseline value – Baseline value.

Relative change from baseline will be calculated and expressed in percentage as 100% × (Postbaseline value – Baseline value)/Baseline value.

Treatment-emergent (TE) Period

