8.3 Efficacy Analysis

Statistical methodology will be restricted to descriptive statistics only. Unless specified otherwise, all efficacy analyses described in this section will be based on the FAS, for the Ivacaftor Arm overall.

The analysis will include all available measurements per the visit windowing rules described in [Appendix B](#).

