⁵¹ MBW will be performed on subjects for whom additional or separate informed consent was obtained for the procedures, and only at sites that are adequately trained and qualified to perform this assessment (CSP Section 11.5.6). The Day 1 MBW must be performed within 1 week before the first dose, not postdose. The Week 96 MBW must be performed within 1 week before the last dose, not after the last dose. Detailed procedures will be supplied in a separate study manual.

⁵² MBW will be performed at the Week 48 and Week 72 Visits (± 7 days).

⁵³ The morning dose of study drug will be administered at the Day 1, and 2-, 4-, 8-, 12-, 18-, and 24-Week Clinic Visits. After the Week 24 Visit, the morning dose need not be administered at the Clinic Visit. Additional guidance for preparation and administration of study drug is provided in CSP Section 9.4 and the study manual.

Table 11-3 Schedule of Assessments for VX15-770-126 (Ivacaftor Arm: Study 124 Part A Only Subjects or Subjects Not From Study 124)

Event/Assessment	Screening Period ³⁵	Treatment Period (Day 1 through Week 96)								ETT Visit ³⁶	Safety Follow-up Visit ³⁷	24-Week Follow-up OE
	Day -28 to Day -1	Day 1	Day 3 (± 1 Day)	Week 2 (± 1 Day)	Week 4 (± 5 Days)	Weeks 8 and 18 (± 7 Days)	Weeks 12 and 24 (± 7 Days)	Weeks 36, 60, and 84 (± 7 Days)	Weeks 48, 72, and 96 (± 7 Days)	As Soon as Possible After the Last Dose	4 Weeks (± 7 Days) After the Last Dose	24 Weeks (+ 14 Days) After the Last Dose
Adverse events	Continuous from signing ICF through the Safety Follow-up Visit (see CSP Section 13.1.1.3)										Ocular adverse events only	
Medications and procedures review	Continuous from signing of ICF through the Safety Follow-up Visit											

CF: cystic fibrosis; *CFTR*: CF transmembrane conductance regulator gene; ETT: Early Termination of Treatment; ICF: informed consent form; MBW: multiple breath washout; LFT: liver function test; OE: ophthalmologic examination; q12h: every 12 hours.

Appendix B: Analysis Visit Windows for Safety and Efficacy Assessments**Table 11-4 Analysis Visit Windows for Safety and Efficacy Assessments - Rollover Subjects From Study 124 Part B or Part A/B**

Assessment	Visit ^a	Target Study Day	Analysis Visit Window (in study days)
Safety Assessments			
Serum Chemistry Hematology Vital Signs	Baseline	Not applicable	parent study baseline
	Week 12	84	[2, 126]
	Week 24	168	[127, 210]
	Week 36	252	[211, 294]
	Week 48	336	[295, 378]
	Week 60	420	[379, 462]

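### For rollover children the SAP drops, without declaring it, the change from the Study 126 baseline that Protocol 12.3.1 specifies, so change from Day 1 of this study is not tabulated

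*Protocol*

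**What the plan says.** Protocol 12.3.1 sets up two baselines and assigns them by route of entry. For Same-day rollovers, "absolute change will be determined from Study 124 Part B baseline and Study 126 baseline". For Part B subjects "with a Gap Transition (Section 9.1.1.2.1), absolute change will be determined from Study 126 baseline". The section applies these definitions to efficacy and safety variables alike, unless otherwise specified.

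SAP 8.1 also names two baselines but assigns them differently. The rollover baseline "is defined as the baseline measurement from Study 124 Part B or Part A/B", with no split between Same-day and Gap. The other is reserved for children new to the drug: "Study 126 baseline: the baseline value for IVA-naïve subjects (who did not participate in Study 124 Part B or Part A/B".

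SAP Appendix B, Table 11-4 (rollovers) follows 8.1. The baseline row for every assessment reads "parent study baseline", and the first window after it opens on Day 2. SAP 8.2.2 takes rollover baseline characteristics from Study 124. SAP 8.3 ties the efficacy tables to the windows: "The analysis will include all available measurements per the visit windowing rules described in" Appendix B.

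SAP 2.1 records changes to the protocol, some as small as an endpoint name. It declares that rollover and other subjects will be combined, but says nothing about the Study 126 baseline for rollovers.

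**The concern.** The objectives are long-term safety and pharmacodynamics. A Same-day child starts Study 126 at the Week 24 Visit of Study 124 Part B, so what this study adds for that child is the course from Day 1 to Week 96. The protocol provided for that comparison. Under the SAP, the planned tables show only the change from the pre-drug value in the earlier study, which includes the initial response.

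The conflict is sharper for Gap children, because the SAP replaces the only reference the protocol names for them with one the protocol does not use for them. Their Day 1 measurements are largely taken afresh for this study: "All Day 1 assessments will be conducted on Day 1 with the possible exception of the serum and hematology assessments and the OE". Those measurements would then appear in no baseline or by-visit table.

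Because the departure is undeclared, a reader of the final report could take the tabulated change for the one the protocol specified.

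**Working it through.** No stated figure depends on this point, and the planned 75 subjects come without a formula, so there is no plan figure to reproduce. The check compares the texts and tests which days the windows cover.

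**Step 1: baseline by route of entry.**

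| Subjects | Protocol 12.3.1 | SAP 8.1 and Appendix B |
|---|---|---|
| Same-day rollovers | Study 124 and Study 126 | Study 124 only |
| Gap rollovers | Study 126 only | Study 124 only |
| Not from Part B | Study 126 | Study 126 |

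Only the last row agrees.

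**Step 2: days covered by Table 11-4 (rollovers).**
- Chemistry, hematology, vital signs and growth: Days 2–126, 127–210, 211–294, 295–378, 379–462, 463–546, 547–630, and 631 to at least 686.
- ECG, ophthalmologic examination, fecal markers, sweat chloride, microbiology and multiple breath washout: Days 2–252, 253–420, 421–588, and 589 to at least 686.

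In both sets the only uncovered day from 1 to 686 is Day 1. In Table 11-5 (IVA-naïve subjects) the baseline window is Day 1 or earlier, so Day 1 is covered there.

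**Step 3: time span of the tabulated change.** A Same-day child has completed 24 weeks of Part B on Day 1, so time since the Study 124 baseline is 24 plus the nominal Study 126 week.

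| Study 126 visit | Weeks since Study 124 baseline | Share before Study 126 |
|---|---|---|
| Week 24 | 24 + 24 = 48 | 24/48 = 50% |
| Week 48 | 24 + 48 = 72 | 24/72 = 33% |
| Week 72 | 24 + 72 = 96 | 24/96 = 25% |
| Week 96 | 24 + 96 = 120 | 24/120 = 20% |

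At Week 96 that is 840 days, against 96 × 7 = 672 days from Day 1. For Gap children the span is longer by an interval the documents do not state.

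**Step 4: what can still be recovered.** Let B be a child's Study 124 baseline and Y the value at a Study 126 visit. Then (Y at Week 96 − B) − (Y at Week 24 − B) = Y at Week 96 − Y at Week 24. B cancels, so for children measured at both visits the drift after Week 24 follows from the by-visit rows. The step from Day 1 to Week 24 needs Y at Day 1, which no by-visit or baseline table holds.

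**Step 5: does another section restore it?** SAP 8.3.2 mentions a Study 126 baseline for sweat chloride but does not assign one to rollovers, and 8.1 limits it to IVA-naïve subjects. SAP 2.1 is silent.

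**The case against.** The protocol leaves some room. Section 12 defers detail to the SAP, 12.3.3.2 and 12.3.3.3 allow summaries by treatment duration or by time on study, and 12.3.1 ends with an exception clause. A pre-drug baseline is also a defensible pharmacodynamic reference. This supports keeping the Study 124 baseline. It does not explain why the other reference is absent or why SAP 2.1 omits the change.

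Three stronger readings are tempting, and the documents do not support them.
- A reader might infer that Day 1 values are lost altogether. They appear in the individual listings (SAP 8.1). Because the treatment-emergent period starts on the first dose date, a Day 1 liver test or ECG may also count in the threshold tables (SAP 8.4.2 and 8.4.3).
- A reader might infer that nothing is measured from the start of this study. Treatment-emergent adverse events, annualized exacerbation and hospitalization rates, and time to first event all run from the first Study 126 dose.
- A reader might infer that waning of the sweat chloride response would go unseen. Drift after Week 24 can be derived from the by-visit rows, as step 4 shows. Pooling with IVA-naïve children makes those rows harder to read, but SAP 2.1 declares the pooling and it is a separate matter.

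It is also fair to say that Gap children do not fit a rationale of maintained response. Table 3-2 footnote e allows for children who completed the Study 124 Safety Follow-up Visit before screening, so their Day 1 value may be off drug, and change from it may reflect re-treatment. That calls for a separate display.

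**Conclusion.** The point holds as an undeclared departure from Protocol 12.3.1, limited to change-from-baseline variables in rollovers: sweat chloride, growth, fecal markers, LCI, laboratory values, ECG and vital signs. For these, change from Study 126 Day 1, including the Day 1 to Week 24 step, is not tabulated. For Gap rollovers the protocol's only named reference has been replaced.

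Its size is structural: one uncovered day, and a Week 96 change spanning about 120 weeks instead of 96 in Same-day children. The 120 weeks assume that the full 24 weeks of Part B were completed.

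A reader might want to express the loss as precision in mmol/L. The documents give neither a standard deviation nor the number of rollovers. An interval for total response from the pre-drug value and one for change over the extension also describe different quantities. Since Protocol 12.3 plans no inferential analyses, no such figure is offered. The matter should be corrected, but it does not undermine the primary safety analysis.

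**What to change.** 1. Keep the Study 124 baseline for rollovers as the SAP has it.
2. In SAP 8.1, also define a Study 126 baseline for rollovers: the last non-missing value on or before the first Study 126 dose. For Same-day children this is the Study 124 Week 24 / Study 126 Day 1 record. A rule of study day 1 or earlier would be too loose, because every earlier Study 124 record also meets it.
3. Add this baseline as a Day 1 row in Table 11-4.
4. Tabulate change from it by visit for rollovers, for the variables named above. Show Same-day and Gap children separately, because Gap Day 1 values may be off drug.
5. Record any remaining departure from Protocol 12.3.1 in SAP 2.1, with the reason. If the omission was deliberate, this entry is still needed.

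The assessments are already scheduled. The cost is SAP wording and some extra descriptive tables; the drawback is longer output.
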